#### 4.4. Follow-up period

- After enrollment, clinical follow-up will be conducted every 4 weeks for the first 3 months after viral treatment. After 3 months, follow-up visits can be performed by phone, images and blood tests results can be sent by email, or patients can come to our hospital for treatment and follow-up if they wish. Treatment tolerability was measured by severity classification of adverse events (NCI-CTCAE V5.0) and correlation with the investigating drug.
- Visit 1: 28±5 days after Ad-TD-nsIL12 injection. Including:
  - Physical examination, including vital signs, weight, and height.
  - Neurological examination and functional status assessment (LPS or KPS);
  - Quality of Life Assessment (PedsQL™);
  - Laboratory blood tests, some of which will be retained for subsequent analysis;
  - MRI (with or without gadolinium) and tumor response assessment;
  - Evaluation and documentation of adverse events, concomitant medications;
  - Steroid evaluation.
- Visit 2: 8±1 weeks after Ad-TD-nsIL12 injection. Including:
  - Physical examination, including vital signs, weight, and height.
  - Neurological examination and functional status assessment (LPS or KPS);
  - Quality of Life Assessment (PedsQL™);
  - Laboratory blood tests, some of which will be retained for subsequent analysis;
  - MRI (with or without gadolinium) and tumor response assessment;
  - Evaluation and documentation of adverse events, concomitant medications;
  - Steroid evaluation.
- Visit 3: 12±1 weeks after Ad-TD-nsIL12 injection. Including:
  - Physical examination, including vital signs, weight, and height.
  - Neurological examination and functional status assessment (LPS or KPS);
  - Quality of Life Assessment (PedsQL™);
  - Laboratory blood tests, some of which will be retained for subsequent analysis;
  - MRI (with or without gadolinium) and tumor response assessment;
  - Evaluation and documentation of adverse events, concomitant medications;
  - Steroid evaluation.
- Visit 3 is the last designated clinical follow-up, after which the patient's overall AE will be concluded and assessed.
- Except for the 3 planned visits, both patients and investigators may request unplanned follow-up at any time.
- During follow-up, if viral infection of CSF is suspected, the investigator will decide whether to perform virological (AdV) testing.

#### 4.5. Remote follow-up

- Remote follow-up contact: (6 months ± 1 month, 12 months ± 1 month, 18 months ± 1 month, 24 months ± 1 month)
- Visit :
  - Survival;
  - Assessment of quality of life;

- Evaluation and documentation of adverse events, concomitant medications;
- Steroid use;
- If any imaging tests are performed, radiological information is collected and analyzed.
- After that, patients will continue to receive standardized treatment for DIPG, and investigators will continue to follow up on their basic information, including but not limited to survival, quality of life, and occurrence of AE. Depending on the special and necessary clinical situation, the investigator may request increased follow-up frequency, or even follow-up in Sanbo Brain Hospital.
- At the time of tumor progression, the study will end, the patient and their guardians could chose following treatment, and the investigators will continue to collect basic information about clinical status (including at least survival and quality of life assessment) until the patient dies or at least 2 years after virus injection.
- If the tumor does not progress, the investigators will continue to collect basic information about clinical status (including at least survival and quality of life assessment) until the patient dies or at least 5 years after virus injection. Again, researchers can decide to conduct a final analysis of the study data or to continue long-term follow-up of certain patients at any time, this decision that can only be made after all patients have died or been followed for more than 1 year.

#### **4.6. Follow-up of laboratory tests**

Basic blood tests will be done before and early (within 3 days) after virus injection, and during 1 to 3 visits. These tests will include, but are not limited to:

- Hematology: white blood cell count with differential, including neutrophils, lymphocytes, monocytes, eosinophils and basophils, red blood cell count, hemoglobin, hematocrit, platelets, mean platelet volume (MPV), MCV, MCH, MCHC, RDW.
- Chemical and C-reactive proteins: glucose (fasting), creatinine, sodium, potassium, chloride, calcium and C-reactive proteins.
- Coagulation: PT, APTT

#### **4.7. Radiological follow-up**

- MRI will be used to evaluate tumor response, and assessment of tumor reflection requires a uniform sequence from baseline (T2 or enhanced phase recommended).
- Time point
  - Within 15 days before Ad-TD-nsIL12 injection (baseline);
  - Within 3 days after Ad-TD-nsIL12 injection;
  - Visit 1 (28±5 days after Ad-TD-nsIL12 injection);
  - Visit 2 (8±1 weeks after Ad-TD-nsIL12 injection);
  - Visit 3 (12±1 weeks after Ad-TD-nsIL12 injection).
- The RAPNO criteria (2020) will be used to assess tumor response. If a pseudoprogression is suspected according to image changes within the first two months after viral injection, the final verdict will be made by a radiologist based on the advanced MRI sequence. After the final planned MRI is completed (Visti 3), the study procedure will be completed, after which the patient will continue to receive standardized treatment, and the investigator will continue to follow up with basic information, including but not limited to survival, quality of life, and occurrence of AE.
- Researchers can request an MRI at any time during the study to determine the imaging response of the tumor.

#### **4.8. Dose escalation and determination of the maximum tolerated dose**

**(MTD).**

- The dose will start with  $3 \times 10^9$ vp. Three dose stages are planned:  $3 \times 10^9$ vp,  $1 \times 10^{10}$ vp as well  $3 \times 10^{10}$ vp.
- Each cohort will include 3 to 6 participants depending on the occurrence of AE. The criteria for dose climbing are as follows:
  - If there were no Ad-TD-nsIL12 related SAEs (NCI-CTCAE  $\geq$  grade 3) occurred within 6 days after virus injection in the previous patient in the same cohort, the latter patient continues to be included.
  - If 1 patient developed Ad-TD-nsIL12 related SAE in a cohort, 3 patients will continue to be included in this cohort to verify whether it's accidental, and if any 1 of the subsequent 3 patients developed Ad-TD-nsIL12 related SAE, it would be considered as the dose limiting toxicity (DLT), and the previous dose is taken as the maximum tolerated dose (MTD).
  - If 2 patients in the same cohort developed investigational drug-related SAE, it will be considered to be DLT, then the trial will be terminated and the dose used in previous cohort will be defined as MTD.
  - If all 3 patients in the same cohort had no drug-related SAE within 10 days after virus injection, the dose would be upgraded to the next cohort.
  - If DLT presented in the first cohort (D1), dose adjustment will be made according to what is described in protocol 4.3, and if DLT still occurs at D0, the trial terminates.
  - If DLT still does not occur at the highest dose D3, MTD is not defined and the trial terminates.
- Any clinical SAEs deemed to be likely to be associated with Ad-TD-nsIL12 will be recorded by the investigator and graded accordingly. Follow-up will continue until the SAE disappears or drops to grade 1.
- In addition, if non-neurological complications related to any surgical or anesthesia management occur (including, but not limited to, respiratory failure, pneumonia and other systemic infections, cardiac arrest, myocardial infarction, pulmonary embolism, deep vein thrombosis, tracheal and laryngeal trauma, postanesthesia lethargy, fatigue, and short-term memory loss), dose reduction may be considered after discussion with the principal investigator.

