## **10. Statistical methods**

### **10.1. Study endpoints**

- Primary endpoint  
The maximum tolerated dose (MTD) of Ad-TD-nsIL12. (According to the criteria of NCI-CTCAE V5.0, MTD will be defined as doses below the dose that causes DLT. If no DLT has occurred at D3, the trial is terminated and MTD is not defined.)
- Secondary endpoints  
Tumor response based on tumor size change on continuous MRI scans after injection, time to progression, viral activity based on sample analysis, and immunogenicity based on adenovirus antibodies in serum. Overall survival of the patient. Due to the small number of participants, it is expected that the secondary endpoint will only be used to provide reference trends for future phase II efficacy studies.

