### **10.2. Estimation of sample size**

Sample size was determined by the incidence of DLT in three dosing cohorts, each with 3 to 6 assessable participants. If DLT is not observed, at least nine participants will be included if MTD is not reached. Admission to nine participants was expected to take 10

to 12 months; 18 patients about 15-20 months.

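### A dose can be declared the MTD on three patients alone, because no rule fills it to six and the two-event rule ends the trial first

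*Protocol*

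**What the plan says.** Section 4.1 calls the trial a 3+3 dose escalation. Section 4.8 plans D1 = 3×10^9, D2 = 1×10^10 and D3 = 3×10^10 vp, with 3 to 6 patients per cohort depending on adverse events. The rules in 4.8 that matter here are:

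- Three clean patients move the trial up: "If all 3 patients in the same cohort had no drug-related SAE within 10 days after virus injection, the dose would be upgraded".
- After one drug-related SAE, three more patients join the cohort; any further event among them rejects the dose, "and the previous dose is taken as the maximum tolerated dose (MTD").
- After two such events in a cohort, "then the trial will be terminated and the dose used in previous cohort will be defined as MTD".
- At the top dose, "If DLT still does not occur at the highest dose D3, MTD is not defined and the trial terminates".

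Section 10.1 makes the MTD the primary endpoint and repeats the rule: "MTD will be defined as doses below the dose that causes DLT". Sections 1.6 and 10.2 plan 9 to 18 patients in three cohorts of 3 to 6. No section sets a minimum number of patients at the dose that is named, or sends patients back to it.

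**The concern.** A cohort grows to six only if one of its first three patients has an event. A clean cohort of three is left behind at once. If the next dose then fails, the trial returns to that cohort in name only. The plan rejects a dose on 2 events in 6, but the dose it declares tolerated need never face that six-patient test. The plan adds three patients to see whether a single event was chance; it does not ask the same of three clean patients.

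The case is foreseeable. Section 2.3 reports an earlier study of the same product in recurrent glioblastoma, with MTD 1×10^10 and next dose 5×10^10 vp. D3 here lies between the two, so DLT at D3 with D2 named is a realistic course. At stake is how much evidence stands behind the primary result. The safety committee in section 8.1 can change or stop recruitment after a dose-related SAE, but nothing ties it to the evidence for the MTD.

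**Working it through.** **Inputs.** The rules and the range 9 to 18 come from 1.6, 4.8, 10.1 and 10.2. The Protocol gives no true DLT rates and no target rate; every rate below is an assumption. Write p for the true rate at a dose and q = 1 − p.

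**1. The plan's own figure.** 3 × 3 = 9 and 3 × 6 = 18, as stated. To reach 18, D1 and D2 must each go to six and still escalate, so the total implies that 1/6 may escalate, although 4.8 does not say so. Read literally (only 0/3 escalates), D1 to D3 could take at most 3 + 3 + 6 = 12.

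**2. Share of named MTDs that rest on 0/3, batch reading (three, then three more).** A dose is passed on 0/3 with probability q³, and on 1/6 with probability 3pq² × q³ = 3pq⁵. The failure probability of the next dose cancels, so

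share = q³ / (q³ + 3pq⁵) = 1 / (1 + 3pq²).

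The term 3pq² is largest at p = 1/3, where it is 4/9. The minimum share is 1/(1 + 4/9) = 9/13 = 69.2%. It is 80% at p = 0.10, 72% at 0.20 and 73% at 0.50. The share over D1 and D2 together is a weighted mean of the two, so the bound holds for any rates. If 1/6 may not escalate, the share is 100%.

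**3. Share if the three further patients are counted from the first event (4 to 6 in total).** The share is 1/(2 − q³): 79% at p = 0.10, 67% at 0.20, 59% at 1/3 and 53% at 0.50.

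**4. What 0/3 says.** Exact one-sided 95% upper limits for the DLT rate:

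| Result | Upper limit |
|---|---|
| 0/3 | 1 − 0.05^(1/3) = 63% |
| 1/6 | 58% |
| 0/6 | 1 − 0.05^(1/6) = 39% |

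**5. What filling would do.** Three more patients reject a 0/3 dose if at least two have DLT, with probability 3p²q + p³: 2.8% at p = 0.10, 6.1% at 0.15, 25.5% at 0.33 and 50% at 0.50.

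**6. Worked case: D1/D2/D3 at 10/33/50%, 1/6 may escalate.**
- D1 passes: 0.7290 + 0.1771 = 0.9061.
- D2 passes: 0.3008 (0/3) + 0.1337 (1/6) = 0.4344, up to rounding.
- D3 fails: 0.8281.
- D2 named now: 0.9061 × 0.8281 × 0.4344 = 32.6%.
- D2 named after filling: 0.9061 × 0.8281 × (0.3008 × 0.7452 + 0.1337) = 26.8%.
- Share of named MTDs on 0/3: 0.638/0.8385 = 76.1%.
- Mean number treated at D1 to D3: 9.28, rising to 11.33.

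**7. Other assumed rates, over all trials.**

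| D1/D2/D3 (%) | MTD named on 0/3 | D3 passes, no MTD | Mean extra patients if filled |
|---|---|---|---|
| 10/33/50 | 64% | 7% | 2.1 |
| 5/15/40 | 57% | 25% | 1.8 |
| 5/10/20 | 29% | 63% | 0.9 |
| 3/5/10 | 10% | 87% | 0.3 |

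At 5/40/60% the mean rise is 2.5. At 5/15/40%, naming an acceptable D2 falls from 54.7% to 52.2%.

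**The case against.** **It is a design choice.** Sections 4.8, 10.1 and 10.2 agree with one another on this point, and naming the previous dose without filling it is one version of 3+3. That stands: nothing is contradicted, and with no target rate the only benchmark is the plan's own rejection at 2 of 6. The point is that the rule fixes the primary endpoint weakly.

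**The gain is small for the children it uses.** At 10/33/50% filling cuts naming of the 33% dose by 5.8 percentage points for 2.05 extra children, about 2.05/0.058 = 35 per wrong naming avoided. Each has biopsy, reservoir and virus before any other treatment (4.3, 4.10). A cohort ending at 1/6 has an upper limit of 58%, barely below 63%. This stands, and it is why a reporting-only remedy is offered.

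**A reader might take 69% as a bound under any reading.** It is not. It needs the batch reading; step 3 gives lower shares. The batch reading is the better fit, since 4.1 says 3+3 and 4.3 speaks of 2 or 3 patients at D1 and then the next 3, but 4.8 does not exclude the other.

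**A reader might infer that 10.1 carries the MTD into phase II.** The words "provide reference trends for future phase II efficacy studies" refer to the secondary endpoints only. No section makes the MTD a recommended phase II dose.

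**A reader might infer that D2 would rest on three patients and nothing else.** D2 equals the MTD of the earlier study, which supports it in part. That study had 8 patients over three doses, in recurrent glioblastoma.

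**Conclusion.** The concern holds, as a moderate weakness in the rule for the primary endpoint. The text lets a dose become the MTD on three patients, and after two events at the next dose it closes the trial before that can be mended. If an MTD is named at D1 or D2, three patients are the usual basis: at least 69% of cases under the batch reading with 1/6 escalating, all cases if 1/6 may not escalate, and a smaller majority at the rates shown (53% to 79%) if patients are counted from the first event. The upper limit of 63% at 0/3 depends on none of these readings.

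The point does not arise when D3 passes, which is the most likely outcome if the product is well tolerated (87% at 3/5/10%). An MTD at D0 is outside these figures. The benefit of filling depends on the assumed rates and lies mainly in a second chance to reject a toxic dose. The rule should be changed, or at least the reporting, but the defect does not invalidate the trial.

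**What to change.** In the two-event bullet of 4.8, replace the instruction to end the trial with *escalation stops*. In 4.8 and 10.1 add:

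> *If the previous dose has only three assessable patients, up to three more are treated there, within the planned total of 18. It is the MTD if at most 1 of 6 has DLT; otherwise the next lower dose is assessed in the same way. If D1 fails, the D0 rule of 4.3 applies if places remain; otherwise no MTD is defined.*

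Say also how *assessable* fits with 4.9, under which patients who withdraw are not replaced.

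If the cohort is not filled, report the dose as provisional, with the number treated, the number with DLT and the exact upper limit. This needs no extra patient and is the minimum change.

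**Cost.** A few lines of text. Filling adds 0.3 to 2.5 children per trial on average under the assumed rates, up to three per step down; D1 to D3 together never exceed 18. On time, 10.2 says "Admission to nine participants was expected to take 10" to 12 months, and 18 patients about 15 to 20. Three patients then take about 3 × 15/18 = 2.5 to 3 × 12/9 = 4.0 months of a 2-year study. An acceptable D2 is named slightly less often, and a provisional label gives a less firm headline.

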## **4. Study design**

### **4.1. Overall design**

Single-arm, single-center, drug safety assessment clinical trial with a 3+3 dose escalation design.

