### 4.3. In-hospital period

- After stereotactic biopsy, the Ommaya reservoir will be inserted through the biopsy channel and a single injection of Ad-TD-nsIL12 will be delivered immediately after surgery.
- The injection dose start with  $3 \times 10^9$ vp (D1) and follow  $1 \times 10^{10}$ vp (D2),  $3 \times 10^{10}$ vp (D3) for climbing. If 2 or 3 patients develop severe adverse event (SAE) according to NCI-CTCAE at D1. The dose will then be reduced to  $1 \times 10^9$ vp (D0). If one patient develops SAE at the D1 dose, the other 3 patients will continue to be included with the D1 dose to assess whether the occurrence of this SAE is accidental. If SAE develops in 1 of the next 3 patients, following patients will receive the D0 dose.
- Before subsequent patients enrollment, the former patient in each cohort must be observed for at least 6 days after virus injection. The administration of virus to participants in the new cohort will be at least 10 days behind the last participant in the previous cohort.
- If the patient presents with symptoms of decreased brain function or decreased cardiovascular perfusion, or if there is an allergic reaction or signs of anaphylaxis, administration of Ad-TD-nsIL12 should be discontinued. In addition, treatment of Ad-TD-nsIL12 will also be interrupted if other AEs deemed necessary by investigators to be interrupted. In addition, if ventricular penetration is considered to have occurred during viral use, the dosing procedure will be terminated and no further treatment with Ad-TD-nsIL12 will be given, and such patients will be observed and examined by virologic testing (AdV) and further follow-up.
- The tumor tissue obtained at the time of biopsy or excision, as well as the collected blood samples, will be archived in our hospital for future analysis.
- Visit 0:  $3 \pm 1$  days after Ad-TD-nsIL12 injection. Including:
  - Physical examination, including vital signs, weight, and height;
  - Neurological examination and functional status assessment (LPS or KPS), life quality assessment;
  - Blood tests, blood biochemistry (containing C-reactive protein), coagulation function assessment and other blood tests (including detection of adenovirus antigens and anti-adenovirus antibodies in serum);
  - MRI (with or without gadolinium) and tumor response assessment;
  - Assessment and documentation of adverse events, including concomitant medications, including steroids.

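### Sections 4.3, 4.8 and 10.1 are not reconciled for the branch that moves down from D1 to D0, so the same data can give conflicting conclusions on the MTD

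*Protocol*

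**What the plan says.** Section 4.1 describes a "drug safety assessment clinical trial with a 3+3 dose escalation design". Under section 4.8, "Three dose stages are planned" (D1, D2 and D3), and "Each cohort will include 3 to 6 participants depending on the occurrence of AE". D0, the reduced dose, appears only in section 4.3 and in the fallback bullet of 4.8.

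These rules bear on the D0 branch:

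- **Opening D0 (4.3).** Two or three SAEs at D1 reduce the dose to D0. One SAE in the first three leads to three more patients at D1, and then: "If SAE develops in 1 of the next 3 patients, following patients will receive the D0 dose".
- **Two events in a cohort (4.8).** This counts as DLT, "then the trial will be terminated and the dose used in previous cohort will be defined as MTD". For one event followed by another in the expansion, 4.8 likewise takes the preceding dose as the MTD.
- **Clean cohort (4.8).** If all three patients "had no drug-related SAE within 10 days after virus injection, the dose would be upgraded to the next cohort".
- **D0 bullet (4.8).** After DLT at D1 the dose is adjusted as in 4.3, and "if DLT still occurs at D0, the trial terminates".
- **Endpoint definition (10.1).** "MTD will be defined as doses below the dose that causes DLT". The only case in which 10.1 declares the MTD undefined is no DLT at D3.

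**The concern.** Section 4.8 refers to the preceding dose, the preceding cohort and the next cohort. While the trial climbs, the preceding cohort is also the next lower dose, so cohort order and dose order agree. On the D0 branch they part: the cohort treated just before D0 is D1, a higher dose that has already met the DLT rule. The general bullets contain no exception for this.

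The primary endpoint and patient safety are both at stake. Two readers applying the protocol to the same record could report different MTDs. One literal path also leads back to a dose that has just met the DLT rule. These rules govern enrolment and dosing as the trial runs, so they need to be settled in the protocol itself.

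**Working it through.** **The plan's own figure.** Three cohorts of 3 to 6 give 3 × 3 = 9 and 3 × 6 = 18, which reproduces the stated 9 to 18 patients. D0 is not counted in that range.

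**Tracing the rules.** Suppose D1 has met the DLT rule and D0 is open.

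| Outcome at D0 | 4.8, general bullets by cohort order | 4.8, D0 bullet | 4.3 | 10.1 |
|---|---|---|---|---|
| 0 of 3 | Escalate; the next dose up is D1 | Silent | Later patients receive D0 | MTD below D1, so D0 |
| 1 of 3, then 0 of 3 | No rule | Silent | Later patients receive D0 | MTD below D1, so D0 |
| 1 of 3, then at least 1 of 3 | MTD is the preceding dose: D1 by time, none by dose level | Trial ends; no MTD stated | Silent | Nothing lower than D0 exists; D1 excluded |
| At least 2 of 3 | Trial ends; MTD is the preceding cohort's dose: D1 by time, none by dose level | Trial ends; no MTD stated | Silent | Nothing lower than D0 exists; D1 excluded |

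The first row is a direct conflict between the escalation bullet and the other two sections. The last two rows conflict with 10.1 only if the general bullets still apply at D0 and are read by time. Otherwise they leave the MTD unstated.

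**How often the branch arises.** The protocol gives no DLT rates, so those below are assumptions. With true rate p in a cohort:

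P(DLT rule met) = P(at least 2 of 3) + P(1 of 3) × P(at least 1 of next 3)

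- p = 0.10: 0.028 + 0.243 × 0.271 = 0.094
- p = 0.20: 0.104 + 0.384 × 0.488 = 0.291
- p = 0.30: 0.216 + 0.441 × 0.657 = 0.506
- p = 0.40: 0.352 + 0.432 × 0.784 = 0.691

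These are the chances that D0 opens. For the outcome at D0, take its rate as half that at D1 (a further assumption). P(0 of 3) = (1 − p)³, and P(1 of 3, then 0 of 3) = 3p(1 − p)² × (1 − p)³.

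| Rate at D1 / D0 | D0 opens | Given D0 opens: 0 of 3 | 1 of 6 | DLT at D0 | All trials: opens, 0 of 3 | All trials: opens, DLT at D0 |
|---|---|---|---|---|---|---|
| 0.10 / 0.05 | 0.094 | 0.857 | 0.116 | 0.027 | 0.080 | 0.002 |
| 0.20 / 0.10 | 0.291 | 0.729 | 0.177 | 0.094 | 0.212 | 0.027 |
| 0.30 / 0.15 | 0.506 | 0.614 | 0.200 | 0.186 | 0.311 | 0.094 |
| 0.40 / 0.20 | 0.691 | 0.512 | 0.197 | 0.291 | 0.354 | 0.201 |

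The split depends on the assumed pairing. With 0.40 at D1 and 0.30 at D0, the last two columns become 0.691 × 0.343 = 0.24 and 0.691 × 0.506 = 0.35.

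**The case against.** The strongest answer is that the D0 bullet governs the whole D1/D0 branch. Under the general two-event bullet, two events at D1 would simply end the trial, with no earlier cohort to supply an MTD. D0 opens only because the later bullet displaces that rule. It would be inconsistent to accept the displacement at D1 and then revive the general bullet at D0. On this reading, DLT at D0 ends the trial and no MTD is named, which agrees with 10.1. The bullets are also introduced as criteria for climbing, where the preceding dose naturally means the lower one. This largely stands. A reader might infer that the protocol names D1 as the MTD after DLT at both doses, but the documents do not support stating that flatly.

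It does not remove the ambiguity. Section 4.3 uses the preceding cohort in a time sense when it sets the 10-day gap between cohorts. The D3 bullet says outright that the MTD is undefined, and the D0 bullet does not.

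For a clean D0 cohort, a reader might infer an instruction to go back to D1. Section 4.3 and 10.1 both oppose that. Section 8.1 also has the safety committee evaluate dose-related grade 3-4 SAEs and change or stop later admission. The planned size gives some further support. If every cohort could expand and still move on, a return through D1, D2 and D3 could take 5 × 6 = 30 patients. If only clean cohorts of three escalate, it could take 6 + 3 + 3 + 3 + 6 = 21. Both exceed 18. With three per cohort, however, it is 5 × 3 = 15, so the stated range does not exclude it. What remains is that the escalation bullet has no exception for D0, and that nothing in 4.8 says what a clean D0 cohort means.

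**Conclusion.** The point holds as a contradiction between sections, not as a clear instruction to name D1 or return to it. The conflict is firmest for a clean D0 cohort, where the literal escalation bullet disagrees with 4.3 and 10.1 and no rule in 4.8 gives the MTD or closes the trial. It is weaker for DLT at D0. There, D1 becomes the MTD only if the general bullet is kept and read by time; on the other reading the MTD conclusion is simply not written down.

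The branch is not remote: it opens in about 9%, 29%, 51% and 69% of trials at assumed D1 rates of 10%, 20%, 30% and 40%. A clean D0 cohort is the likeliest D0 outcome in all four scenarios with the D0 rate at half the D1 rate, but not when the rates are 40% and 30%. These figures show how often the unreconciled text would have to be used. They do not estimate how often a wrong MTD would be reported. Since the MTD is the primary endpoint, the text should be settled before it is needed.

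**What to change.** Reconcile sections 4.3, 4.8 and 10.1 for the D0 branch:

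1. In 4.8, word the MTD and escalation rules by dose level rather than by the order in which cohorts were treated.
2. For each D0 outcome (DLT, and no DLT, including 1 event in 6), state the MTD conclusion and what happens next, consistently with 4.3 and 10.1.
3. Say whether the general two-event and clean-cohort bullets apply on this branch or whether the D0 bullet replaces them.

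Which dose rule applies in each case is for the sponsor to decide; the request is only that the three sections give the same answer. The cost is two or three sentences in 4.8, aligned with 4.3 and 10.1, and ethics committee and sponsor approval of the wording as section 9.4 requires. The clarification itself adds no procedures or data items.

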## **2.3. A study of Ad-TD-nsIL12 in the treatment of recurrent glioblastoma**

Between December 2019 and September 2022, a total of 8 patients were recruited to receive Ad-TD-nsIL12 treatment at the Sanbo Brain Hospital of Capital Medical University. The trial assigned three dose-escalation cohorts ( $5 \times 10^9$ ,  $1 \times 10^{10}$ ,  $5 \times 10^{10}$  vp, 1ml). The most common adverse events were fever and cognitive impairment. Nausea and vomiting also occurred frequently, and the dose used in Cohort 2 ( $1 \times 10^{10}$  vp) was used as the maximum tolerated dose (MTD).

One patient had a complete response after treatment with Ad-TD-nsIL12 and is still alive, while another patient received a partial response. In addition, Ad-TD-nsIL12-related proteins (E1A and hexon) were observed in both post-treatment samples, indicating that Ad-TD-nsIL12 remained active for a longer period of time after surgery. Clearance of the enhancement in the injection area was observed after administration of Ad-TD-nsIL12, and the samples collected also showed higher infiltration of CD3+, CD4+ and CD8+ cells than pre-treatment samples. This is consistent with preclinical studies: the antitumor efficacy of Ad-TD-nsIL12 depends on CD8+ T cells and suggests that Ad-TD-nsIL12 induces a long-term immune response.

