## **8. Adverse event (AE)**

### **8.1. Document of adverse events**

All AEs will be recorded in a Case Report Form (CRF), either during clinical follow-up or voluntarily reported by the patient and their families, and graded according to NCI-CTCAE v5.0. If the investigator determines that a dose-related SAE (grade 3-4) has occurred, the safety committee will evaluate the AE and make changes to the admission of subsequent patients or even stop the recruitment of subsequent participants. AE is recorded until 12 weeks after viral injection as required by the protocol.

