#### **8.6. Report of serious adverse events**

All accidental, life-threatening or fatal incidents related to the research product must be reported in writing to the project sponsor within 24 hours of the event (the next business day). All SAEs defined in the protocol that are considered drug-related must submit a written report to the program sponsor within 5 business days of occurrence. Serious adverse effects must be followed until clinical recovery is complete, laboratory testing returns to baseline, the progression of the event has stabilized, or the event has been acceptably resolved.

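### The day-10 escalation condition has no scheduled assessment behind it, and the Protocol does not say whether a related event after day 10 changes the DLT count of a cleared dose or the MTD

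*Protocol*

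**What the plan says.** **Timing of escalation.** The escalation bullet in Protocol section 4.8 reads "If all 3 patients in the same cohort had no drug-related SAE within 10 days after virus injection, the dose would be upgraded". Section 4.3 adds "The administration of virus to participants in the new cohort will be at least 10 days behind the last participant in the previous cohort". Within a cohort, section 4.3 requires that "the former patient in each cohort must be observed for at least 6 days after virus injection" before the next patient enters.

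**Timing of assessment.** Visit 0 in section 4.3 falls 3±1 days after injection. The next scheduled assessment, in section 4.4, is "Visit 1: 28±5 days after Ad-TD-nsIL12 injection". Sections 4.6 and 4.7 place blood tests and MRI within 3 days of injection and then at Visits 1 to 3. Section 4.4 also allows unplanned follow-up at the request of either side. Under section 8.1, adverse events are recorded "either during clinical follow-up or voluntarily reported by the patient and their families".

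**What counts.** In section 4.8 the rule that one event leads to three more patients, and the rule that two events stop the cohort, have no time window. Nor has the MTD definition in section 10.1. Section 8.1 sends a dose-related grade 3-4 SAE to the safety committee, which may change or stop admission. It records adverse events to 12 weeks.

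**The concern.** The MTD is the primary endpoint in section 10.1, and it depends on how many patients at each dose are counted as having a related SAE. Two things weaken that count.

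First, the decision is tied to day 10 but no scheduled assessment falls near that day. Some of the risks named in the Protocol need active checking: section 7.1 lists hepatitis with abnormal liver tests and brain infection, and section 7.3 describes encephalitis partly by MRI change. After discharge, section 4.3 lets the child be treated at another hospital. A cohort with no recorded event by day 10 may be a cohort that was not asked.

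Second, once a dose has been cleared, the Protocol does not say what a later related event at that dose does to its DLT count or to the MTD. Two analysts with the same data could report different MTDs.

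**Working it through.** **1. The plan's own figure.** Three cohorts of 3 to 6 patients (section 10.2) give 3 × 3 = 9 and 3 × 6 = 18, which matches the 9-18 in section 1.6.

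**2. Gap between scheduled assessments.** Visit 0 ends at 3 + 1 = day 4. Visit 1 opens at 28 − 5 = day 23. Days 5 to 22, which is 18 days, hold no scheduled visit, blood test or MRI. Day 10 lies inside. The 6-day observation reaches day 6, so days 7 to 10 of the decision window have no planned assessment.

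**3. Fastest permitted pace.** With a 6-day stagger, three patients are injected on study days 0, 6 and 12. The next cohort can start on day 12 + 10 = 22. Time since injection is then 22, 16 and 10 days. None has reached day 23.

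**4. Expected pace.** Section 10.2 expects 9 patients in 10-12 months and 18 in 15-20 months. At 30.4 days per month:
- 10 × 30.4 / 9 = 33.8 and 12 × 30.4 / 9 = 40.5 days per patient;
- 15 × 30.4 / 18 = 25.3 and 20 × 30.4 / 18 = 33.8 days per patient.

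At an average of about 25-41 days, even the last patient of a cohort would have entered the Visit 1 window before the next injection. The rules do not require this.

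**5. What an uncounted late event would do.** Let p be the true related-event rate, f the share occurring by day 10, and q = p × f the counted rate. The Protocol gives neither p nor f; both are assumed. I also assume that one event in six patients permits escalation, as in a conventional 3+3 (the bullets of 4.8 do not spell this out), and that later events get no weight. Then

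P(clear) = (1 − q)³ + 3q(1 − q)² × (1 − q)³

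At p = 0.40:

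| Share after day 10 | q | Calculation | P(clear) |
|---|---|---|---|
| none | 0.400 | 0.216 + 0.432 × 0.216 | 0.309 |
| one third | 0.267 | 0.394 + 0.430 × 0.394 | 0.564 |
| one half | 0.200 | 0.512 + 0.384 × 0.512 | 0.709 |

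Range over other assumptions, for f = 1, 0.75, 0.5 and 0.25: at p = 0.33, 0.434, 0.605, 0.783 and 0.933; at p = 0.50, 0.172, 0.351, 0.600 and 0.862.

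**6. The rules side by side.** The escalation bullet stops at day 10. The one-event and two-event bullets and the MTD definition have no limit. Section 8.1 has no limit on committee review, but it speaks of admission and recruitment, not of the DLT count or the MTD. Read literally, the untimed bullets let a day-11 event count. Read with the escalation bullet, the dose has already been cleared. No text chooses between them.

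**The case against.** Several stronger readings are tempting, and the Protocol does not support them.

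- **That later related events have no effect at all.** Section 8.1 lets the safety committee change or stop admission without a time limit, section 8.2 collects study-relevant events at any time, and the DLT bullets are untimed. What is missing is narrower: the effect on a cleared dose's DLT count and on the MTD.
- **That no one looks at the patient after day 4.** Section 4.3 requires at least 6 days of observation between patients and has investigators contact the outside hospital after discharge; section 4.4 allows unplanned follow-up. No discharge day is given. The gap is in scheduled assessment.
- **That a day-10 decision may be taken before events are reported.** Section 8.6 says related SAEs "must submit a written report to the program sponsor within 5 business days of occurrence". That governs written reports to the sponsor. In a single-center trial the investigators may know much sooner, so this argument should not be used.
- **That the 6-day and 10-day periods contradict each other.** They govern different steps: the next patient and the next cohort.
- **That higher doses will routinely open before Visit 1.** This is permitted, but step 4 of the working shows that it is not expected.
- **That section 2.3 shows delayed toxicity.** Its statement that "Ad-TD-nsIL12 remained active for a longer period of time after surgery" rests on viral proteins in post-treatment samples. It says nothing about when toxicity occurs.

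It is also fair to object that the clearing probabilities depend on assumed values and on giving late events no weight. If the untimed bullets do count late events in the MTD, that loss does not follow. What stands after all this is the unsupported day-10 condition and the undefined status of later events.

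**Conclusion.** The point holds in a limited form. The 18-day gap is exact, the day-10 condition falls inside it, and the rules allow a higher dose to open with no Visit 1 data from any patient in a three-patient cohort, though the expected accrual makes that uncommon. The DLT window is stated for escalation and left open for the DLT and MTD rules, so the primary endpoint is ambiguous for a related event after day 10.

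The size cannot be derived from the Protocol. The rise from 31% to 56% or 71% illustrates one reading under an assumed 40% rate and assumed late shares. Its direction holds for any late share that goes uncounted. A reader should not infer that the MTD is already defined to exclude late toxicity; the text does not settle it.

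This is worth correcting because it touches the primary endpoint and patient safety and costs little.

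**What to change.** 1. Add a documented adverse-event contact for each patient (a phone call is enough) that supports the day-10 condition and is on file before escalation.
2. Reconcile sections 4.3, 4.8, 8.1 and 10.1 so that one stated DLT window applies to the escalation, DLT and MTD rules. The separate 6-day stagger between patients can remain a different rule.
3. State what a related SAE after that window does to a dose already cleared and to the MTD.

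The length of the window is for the sponsor and investigators to set. They should note that section 4.3 lets radiotherapy start 2-6 weeks after injection, so from day 14 onwards attribution of an event becomes harder.

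The cost is one extra contact per patient, some wording, and an occasional short delay at a cohort transition.

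Separately, section 2.3 reports that 1×10^10 vp "was used as the maximum tolerated dose (MTD") in the recurrent glioblastoma study, while the third dose in section 4.8 is 3×10^10 vp, three times as high. These sections should be reconciled; this is a different question from the assessment gap and lends it no support.
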